#### **9.4 Protocol Deviations**

In this study, protocol deviations are categorized as follows:

- Informed Consent
- Inclusion/Exclusion Criteria and Concomitant Treatment
- Study Procedures/Treatment, including Study Tests/Assessments/ Laboratory
- Visit Scheduling
- Withdrawal Criteria
- Other

A protocol deviation is considered important if it may affect the study primary endpoints and the subject's rights, safety, or well-being, and/or the completeness, accuracy, and reliability of the study data. Cerus' study team will review all protocol deviations and determine the list of important protocol deviations prior to database lock. All randomized subjects with any important protocol deviation(s) will be tabulated by deviation category for each planned treatment and overall. In addition, protocol deviations will also be listed.

#### **9.5 Prior and Concomitant Medications**

For this study, prior and concomitant medications will be coded using WHO Drug Global B3 (March 2018). Each medication will be classified using the Anatomical-Therapeutic-Chemical (ATC) classification system and mapped to a preferred drug name, summarized for the mITT population.

Subjects taking any prior medications will be tabulated by ATC level 3, level 4, and preferred drug name for each actual treatment received and overall. A subject will be counted at most once for each prior medication, even if the subject took the same prior medication on multiple occasions. Subjects taking any concomitant medications will be tabulated similarly. In addition, prior medications and concomitant medications will also be listed, separately.

#### **9.6 Surgical and Clinical Characteristics**

The following surgical related parameters will be summarized for the mITT population using descriptive statistics:

- Duration of study cardiac surgery
- Time on pump

- Time to discharge
- Volume of cell saver blood
- Use of cell saver blood, platelets, plasma and cryoprecipitate in frequency and percentages

## 9.7 Exposure to Study RBC and Other Blood Product

The extent of exposure to a study RBC is measured by the number and volume of study components as derived in [Section 5.1.3](#). For subjects in the mITT Population, the units of exposure will be summarized using descriptive statistics, and frequency and percentage of subjects will be tabulated by number of study RBC components and total study plus non-study RBC components (1, 2, 3, 4, 5, 6, 7, 8, 9, or  $\geq 10$  units) for subject. Descriptions will be provided for both within the first 48 hours of post-surgery and the entire ASTP period.

## 10. EFFICACY ANALYSES

The primary efficacy analyses will be performed on the mITT population, with subjects classified by planned treatment, irrespective of the actual treatment received.

It may be necessary to complete additional exploratory analyses after the planned analyses are completed. Full details of additional analyses will be presented in the CSR, and any such analyses will be clearly identified as post-hoc.

### 10.1 Analyses of Primary Endpoint

#### 10.1.1 Primary Analyses

The primary efficacy endpoint is the proportion of patients with a diagnosis of renal impairment defined as any raised sCr level, occurring after transfusion of a study RBC, of  $\geq 0.3$  mg/dL (or 26.5  $\mu$ mol/L) from the pre-surgery baseline within  $48 \pm 4$  hours of the end of surgery.

The corresponding hypothesis is:

$$H_0: P_{Test} - P_{Control} \geq 50\% \times \hat{P}_{Control}$$

*versus*

$$H_A: P_{Test} - P_{Control} < 50\% \times \hat{P}_{Control},$$

where  $P_{Test}$  and  $P_{Control}$  are the event rates for Test (INTERCEPT) and Control groups, respectively, and  $\hat{P}_{Control}$  is the observed Control rate.

The primary analysis of the primary efficacy endpoint will be based on Miettinen and Nurminen (M&N) method stratified by baseline sCr ( $sCr \geq 1.2 \text{ mg/dL}$  vs.  $< 1.2 \text{ mg/dL}$ ) and cardiac surgery group performed (more at risk for renal complications vs. less at risk) based on the observed cases.

The maximum observed post-baseline sCr value will be used to calculate the increase from baseline. If subjects have no post-baseline sCr within 48 hours post-surgery at all, this subject will be treated as missing the primary endpoint.

The common risk difference in proportions and the Mantel-Haenszel score 95% CI for the treatment difference (Test – Control) will be calculated using the stratified M&N method adjusting for baseline sCr and cardiac surgery group type. The estimate of the common risk difference will be calculated based on the stratum risk differences across all strata (Agresti, 2002; p. 231). Non-inferiority will be claimed if the upper bound of the 2-sided M&N Score 95% CI for the treatment difference (Test – Control) is less than 50% of the observed Control rate. Further, if the upper bound is less than 0, then superiority is achieved.

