**Table 1: Assessment Schedule**

Study Period	Screening / Randomization		Acute Transfusion Support Period (Surgery to Post-operative Day 7, hospital discharge or death, whichever is first)		Follow-up Visits		
	Screening visit	Baseline (Pre-surgery)	Day 0 Surgery	Days 1 – 7, hospital discharge or death			
Assessment	Window	Day -30 to Day 0	pre-surgery	Day 0 Surgery	Days 1 – 7, hospital discharge or death	28±3 days After last study transfusion or Early Termination	30 days After Surgery
Informed Consent /Assent	X						
Demographics	X						
Indication / Type of scheduled surgery	X						
Medical, surgical, transfusion and medication history including radiographic contrast media within 7 days of surgery / the need for irradiated RBC products	X						
Number of prior pregnancies (females)	X						
Physical examination including height and weight	X						
TRUST score components	X						
Randomization	X #						
Vital signs (HR, BP, RR)	X 	X 	X	X 	X		
Concomitant medications	X	X 	X 	X 	X		
Weekly telephone calls							
EKG	X 	X 	X 	X 			
Pregnancy test (if applicable)	X 	X 					
Hematology panel	X 	X 	X 	X 	X 		
Blood chemistry	X 	X 	X 	X 	X 		
Blood type	X 						
Serum Creatinine at 48±4 hours after end of surgery				X			
Hemodynamic Parameters		X 	X 	X 			
Fibrinogen, Troponin		X 	X 	X 			
Urine output			X 	X 			
Procedure details			X				
Study RBC crossmatch and Study RBC transfusion(s)/data			X	X			

Study Period	Screening / Randomization		Acute Transfusion Support Period (Surgery to Post-operative Day 7, hospital discharge or death, whichever is first)		Follow-up Visits			
	Screening visit	Baseline (Pre-surgery)	Day 0 Surgery	Days 1 – 7, hospital discharge or death				
Assessment	Window	Day -30 to Day 0	pre-surgery	Day 0 Surgery	Days 1 – 7, hospital discharge or death	28±3 days After last study transfusion or Early Termination	30 days After Surgery	End of Study (75±15 days After Last Study Transfusion)
DAT, IAT	X 			X 	X 	X		

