#### **7.1 Handling of Missing Data**

##### **7.1.1 Efficacy Measure**

For the primary analysis of serum creatinine (sCr) increase within 48 hours of surgery start, no imputation is needed for the analysis on observed cases using the Miettinen and Nurminen (M&N). In this case, the maximum observed post-baseline sCr value will be used to calculate the increase from baseline. If a subject has no post-baseline sCr within  $48 \pm 4$  hours post-surgery at all, this subject will be treated as missing the primary endpoint. These missing values will be imputed via multiple imputation in the sensitivity analysis with logistic regression approach.

In the sensitivity analysis with Pattern-Mixture Model (PMM) approach, for subjects who received non-study RBC within 48 hours post-procedure, any sCr values collected after the transfusion of non-study RBC will be censored (i.e., treated as missing). Missing sCr data will be imputed using the Multiple Imputations (MI) approach.

Missing secondary efficacy endpoints will not be imputed.

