**Table 3: Overview of Primary and Sensitivity Analysis Methods**

Primary or Sensitivity	Statistical Method	Analysis Population	Handling of Missing Data
Primary Analysis	Miettinen and Nurminen	mITT	Observed cases
Sensitivity Analyses	Logistic Regression	mITT	Multiple Imputation (MI)
	Pattern Mixture Modeling (PMM)	mITT	Multiple Imputation (MI)

While the Logistic regression with MI is under missing at random (MAR) assumption, a second sensitivity analysis is to assess the sensitivity to departure from MAR assumption. Specifically, a Pattern-Mixture Model (PMM) with delta-adjustment of imputations based on missing not at random (MNAR) assumption will be implemented as follows:

- a. Use MCMC to create monotone missingness first. Then obtain standard multiple imputations under MAR assumptions for missing sCr values using monotone regression. The missing data are filled in and 1000 complete data sets are created.
- b. For each sCr value that had been missing because of censoring after having received non-study RBC within 48 hours post-procedure, regardless of treatment group, adjust these values by adding  $\lambda$  to the imputed values, where  $\lambda = 0.1$  mg/dL.
- c. Each of the 1000 complete data sets will then be analyzed separately using the same M&N method as used for the primary analysis.
- d. The estimates obtained from the M&N method of each complete data set are combined for inference purposes.
- e. Repeat step b, c, d, with  $\lambda = 0.2, 0.3, \dots, 0.5$  mg/dL or until the conclusion is reversed from the primary analysis, whichever comes first. The larger the value of  $\lambda$  that is required to reverse the conclusion of the primary analysis, the more robust the conclusion is considered to be.

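### A subject with one early normal sCr and no sample near 48 hours is an observed non-event in the primary analysis and is not imputed in the logistic sensitivity analysis

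*SAP*

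**What the plan says.** **Endpoint.** Sections 3.2.1 and 10.1.1 count any sCr rise of at least 0.3 mg/dL over the pre-surgery baseline, after a study RBC, within 48±4 hours of the end of surgery. Scoring is on the maximum: "The maximum observed post-baseline sCr value will be used to calculate the increase from baseline" (Section 10.1.1; Section 5.2.2 agrees).

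**Missing endpoint.** Section 10.1.1: "If subjects have no post-baseline sCr within 48 hours post-surgery at all, this subject will be treated as missing the primary endpoint". Section 7.1.1 begins the parallel rule with "If a subject has no post-baseline sCr within" and continues with 48±4 hours. The primary Miettinen-Nurminen analysis uses observed cases without imputation.

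**Sensitivity analyses.** For the logistic analysis, Section 7.1.1 says: "These missing values will be imputed via multiple imputation in the sensitivity analysis with logistic regression approach". For the pattern-mixture model, step a under Table 3 says: "Then obtain standard multiple imputations under MAR assumptions for missing sCr values using monotone regression". Step b adds λ to a narrower group: "For each sCr value that had been missing because of censoring after having received non-study RBC within 48 hours post-procedure".

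**Sampling.** Table 1 lists "Serum Creatinine at 48±4 hours after end of surgery" as a separate assessment. It also marks blood chemistry for daily collection on Days 1 to 7 or until discharge (footnote 6).

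**Per-protocol set.** The listed sCr criterion in Section 6.3 excludes a transfused subject only if no sCr exists after the transfusion and inside the window.

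**The concern.** A maximum over a window shows an event as soon as one value qualifies. It shows a non-event only if observation reaches the end of the window. The missing-data rule does not ask whether it did. A subject with a normal sCr a few hours after surgery who then dies, withdraws or misses the later draws enters the primary analysis as free of renal impairment through 48 hours. Table 1 schedules the sample that would settle the question, but the rule makes no use of it.

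This scoring can remove events but cannot add them. The observed rates are therefore at or below the true ones. The non-inferiority limit moves too, because it is half the observed Control rate. Whether the comparison is distorted depends on whether such subjects are equally common in the two arms, and the SAP plans no table that would show this.

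**Working it through.** **1. Where an early-only non-event goes.** Take a subject with one normal sCr at, say, 6 hours after surgery and none later in the window.

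| Analysis | Treatment of this subject |
|---|---|
| Primary (10.1.1) | Has an in-window value, so observed non-event |
| Logistic with imputation (7.1.1) | Not missing under the rule, so not imputed |
| Pattern mixture, step a | Later value may be imputed under MAR; time points not named |
| Pattern mixture, step b | No λ unless the value was censored after a non-study RBC |
| Per-protocol set (6.3) | Meets the listed sCr criterion if the sample followed the study RBC |

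**2. The plan's own figure.** Inputs from Section 4.3: Control rate 0.30, margin 0.15, true difference 0, two-sided 0.05.

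n per arm = (1.960 + 0.842)² × 2 × 0.30 × 0.70 / 0.15² = 146.5

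The stated 146 per arm gives 79.9% power; 167 and 196 give 84.9% and 90.0%. The sample sizes reproduce and are not in dispute.

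**3. Effect on the rates.** Let f be the share of an arm with only an early sample, and s the share of those subjects' events already visible in it. Then

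observed rate = true rate × [1 − f(1 − s)].

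Neither f nor s is in the SAP; both are assumptions. With s = 0.5 and f = 10% in both arms, a true 30% is observed as 0.30 × (1 − 0.10 × 0.5) = 28.5%, and the limit becomes 14.25 points. At the boundary (45% versus 30%) with f = 10% on Test and 4% on Control: Test 0.45 × 0.95 = 42.75%, Control 0.30 × 0.98 = 29.4%. The difference is 13.35 points against a limit of 14.7.

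**4. Effect on the decision.** 160 per arm (half of the planned minimum of 320 transfused), unstratified Miettinen-Nurminen interval, limit = half the observed Control rate, s = 0.5:

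| f Test / f Control | Non-inferiority claimed, true 45% vs 30% |
|---|---|
| 0 / 0 | 6.0% |
| 10% / 10% | 5.9% |
| 3% / 2% | 6.4% |
| 5% / 3% | 6.8% |
| 10% / 4% | about 8.5% |
| 12% / 4% | 9.9% |

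Entries are from exact enumeration. For 10%/4%, enumeration gives 8.7% and simulations give 8.3% and 8.6%. With true rates of 30% in both arms, power is 78.0% with no such subjects and 75.4% at 10%/10%.

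**5. Dependence on s.** With 146 per arm and a Wald interval, 10% versus 5% raises false claims from 5.8% to 7.9% if half of the events are late, and to 10.5% if all are. For equal shares, treating the limit as known, power falls from 79.9% to 77.0% (f = 10%, s = 0.5), 73.8% (f = 10%, s = 0) or 67.0% (f = 20%, s = 0).

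The roughly 6% starting value arises with no early-only subject at all. It comes from setting the limit on the observed Control rate, which is a separate matter. Only the increments belong to this point.

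**The case against.** A reader might infer that these subjects are never imputed and that no planned analysis could reveal the problem. The SAP does not support that. Step a of the pattern-mixture model works on sCr values, not subjects. Creating monotone missingness presupposes several time points, so a skipped later value may well be filled from earlier ones. The MMRM in Section 10.1.3 does not score an absent visit as a non-event. Early deaths count in the secondary endpoint of mortality or RRT by 30 days. What remains is that the imputed time points are unnamed, the departure-from-MAR shift misses these values, and the analysis closest to the primary one leaves them alone.

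A reader might also infer that the rule biases the trial towards non-inferiority. It does so only if early-only follow-up is more common on Test. The trial is double-blind and the SAP gives no reason to expect that. Balanced loss costs the sponsor power and leaves the false-claim rate essentially where it was.

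The 48±4 hour wording could be read as a 44 to 52 hour window, under which an early-only subject would already be missing. The words any raised, maximum and at all, and the plain 48 hours in Section 10.1.1, favour the cumulative reading. Two tenable readings that classify the same subject differently are still a reason to state one.

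Daily chemistry (which I take to include sCr) and the dedicated 48±4 hour draw should make these cases uncommon. Important deviations are tabulated by arm, and the blinded review in Section 6.3 can add per-protocol exclusions. This limits the size of the problem. It does not change how the primary analysis scores such a subject.

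**Conclusion.** The point holds for the primary and logistic analyses. On the better-supported reading, partial follow-up without a rise is treated as complete follow-up without an event. For the pattern-mixture model the finding is narrower: imputation of the later value is possible but unspecified, and the stress test does not cover it.

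The size is modest and conditional. Balanced occurrence lowers the event rate and costs about 3 points of power at an assumed 10% with half of events late. An excess on Test adds under 1 point to the false-claim rate at 5% versus 3%, and about 2.5 points at 10% versus 4%. The shares and the late-event fraction are assumptions throughout. The change is still worth making before unblinding, because the rule decides the primary endpoint and the data needed are already scheduled.

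**What to change.** 1. Align Sections 7.1.1 and 10.1.1 on one stated window, with its start, its end and whether it is cumulative. The opening sentence of Section 7.1.1 counts 48 hours from the start of surgery and should be brought into line with the rest.
2. Class a subject as incompletely observed if there is no qualifying rise after a study RBC and no sCr in the scheduled 48±4 hour window.
3. In both imputation analyses, impute the 48 hour sCr for these subjects from their earlier values, and name the time points in the imputation model. A subject last sampled at 43 hours is then imputed from a close predictor, so the hard cut costs little.
4. Extend the delta shift in step b to these values.
5. Report the number of these subjects and the reason by arm, with deaths shown separately, since an imputed creatinine after death is hypothetical.

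Keep the primary observed-case analysis otherwise unchanged. Do not simply drop these subjects from it: that would keep early events and remove early non-events, which inflates the rates.

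The cost is SAP wording. Values and times are already collected and multiple imputation is already planned. The downside is slightly wider intervals in the sensitivity analyses.

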#### 4.3 Sample Size Estimation

By assuming the proportion of patients with  $\Delta sCr \geq 0.3 \text{ mg/dL}$  to be 30% in the Control arm and no more than a 50% increase from the Control rate (15%) as the non-inferiority margin, a sample size of  $\geq 292$  patients (146 per arm) will provide approximately  $\geq 80\%$  power to declare non-inferiority at the two-sided 0.05 alpha level, assuming the true treatment difference is zero.

Under the same assumptions, sample sizes of 334 patients (167 per arm) and 392 patients (196 per arm) will provide 85% and 90% power, respectively.

In order to maintain sufficient study power to establish non-inferiority for the primary efficacy endpoint, Cerus plans to transfuse a minimum of 320 subjects and may go up to 400.

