### **7. GENERAL CONSIDERATIONS**

All measures will be summarized by treatment (planned or actual received) descriptively. Continuous variables will be summarized using descriptive statistics such as number of observations (n), mean, standard deviation, median, minimum, and maximum. Categorical variables will be tabulated using frequency (n) and percent (%).

The statistical testing will be conducted at a significance level of 0.05 (two-sided) and the 95% confidence interval will be shown, unless specified otherwise. No statistical testing will be conducted for safety measures.

All data manipulations, descriptive summaries, and statistical hypothesis testing will be performed using Statistical Analysis System (SAS) Version 9.4 or later.

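### Non-inferiority is judged against 50% of the observed Control rate, but the M&N interval carries no sampling error for that limit: if the true Control rate is meant, one-sided type I error is about 6%, not 2.5%

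*SAP*

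**What the plan says.** Section 10.1.1 writes H0 and HA with the estimated Control rate on the right-hand side: Test minus Control is compared with 50% of that estimate. The decision rule follows suit. Non-inferiority is claimed if the upper bound of the stratified two-sided 95% M&N score interval for Test minus Control "is less than 50% of the observed Control rate".

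Section 4.3 takes the event proportion "to be 30% in the Control arm and no more than a 50% increase from the Control rate (15%) as the non-inferiority margin". It gives about 80% or more "power to declare non-inferiority at the two-sided 0.05 alpha level, assuming the true treatment difference is zero" with 292 patients (146 per arm), and adds that "sample sizes of 334 patients (167 per arm) and 392 patients (196 per arm) will provide 85% and 90% power, respectively". The intended recruitment is 320 to 400 transfused subjects. Section 7 repeats the two-sided 0.05 level.

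The SAP makes no allowance for the sampling error of the limit. Section 12 lists the move from CMH to M&N but does not mention a limit that is estimated from the data.

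**The concern.** A hypothesis about parameters should not contain a statistic from the sample that tests it. Apart from the notation, the rule has a variance problem. Requiring the upper limit for p_T - p_C to fall below 0.5 p_C (both observed) amounts to judging p_T - 1.5 p_C against 0. That quantity has variance Var(p_T) + 2.25 Var(p_C), whereas the M&N interval uses Var(p_T) + Var(p_C). The errors reinforce each other: a Control rate that is high by chance both shrinks the observed difference and raises the limit.

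At stake is the primary non-inferiority claim. A Test product exactly at the limit that the plan treats as unacceptable could pass more than twice as often as the nominal level allows. The sample size section also describes a different test from the one planned.

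**Working it through.** **Inputs.** From Section 4.3: Control 30%, margin 50% of that (15 points, so the boundary for Test is 45%), two-sided 0.05 (0.025 on the upper side), true difference 0 for power, sizes of 146, 167 and 196 per arm, and 320 to 400 subjects (160 to 200 per arm). From Section 4.2: 1:1 allocation. From Section 10.1.1: the decision rule. The SAP gives no stratum sizes or stratum rates, so any used below are assumptions.

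**1. Reproducing Section 4.3.** With a fixed margin, n per arm = 2 × 0.30 × 0.70 × (1.96 + z)² / 0.15².
- 80% (z = 0.842): 146.5, rounded up to 147, or 294 in total (stated 292).
- 85% (z = 1.036): 167.6, or 336 (stated 334).
- 90% (z = 1.282): 196.1, or 394 (stated 392).

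Power at the stated sizes is 79.9%, 84.9% and 90.0%. The SAP's figures are therefore right to within two patients, but for a margin held fixed at 0.15.

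**2. Type I error of the Section 10.1.1 rule, normal approximation.** True rates are 30% and 45%.
- Variance in the interval: (0.2475 + 0.2100)/n = 0.4575/n. At n = 146 the SE is 0.0560.
- Variance of p_T - 1.5 p_C: (0.2475 + 2.25 × 0.2100)/n = 0.7200/n. At n = 146 the SE is 0.0702.
- Effective critical value: 1.96 × √(0.4575/0.7200) = 1.562, a one-sided error of 5.9%.

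The sample size cancels, so more patients do not cure it.

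**3. Exact check.** All binomial outcomes were enumerated with the unstratified M&N score statistic. Type I error is at 30% vs 45%, power at 30% in both arms.

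| Per arm | Type I error, observed limit | Type I error, fixed 0.15 | Power, observed limit | Power, fixed 0.15 |
|---|---|---|---|---|
| 146 | 5.92% | 2.46% | 74.9% | 80.2% |
| 160 | 5.98% | 2.59% | 78.0% | 83.7% |
| 167 | 6.00% | 2.51% | 79.4% | 85.1% |
| 196 | 6.01% | 2.46% | 84.5% | 90.2% |
| 200 | 6.01% | 2.59% | 85.3% | 90.7% |

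The same code with a fixed limit holds its level, so the excess comes from the random limit and not from M&N.

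**4. Other Control rates, Test at 1.5 times Control, 146 to 200 per arm.** 20%: 5.6 to 5.7%. 25%: 5.8 to 5.9%. 40%: 6.2 to 6.5%.

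**5. Stratification.** Simulating a four-stratum M&N rule at 146 per arm (400,000 trials, assumed strata) gives 5.9% with equal stratum rates and 5.8% with unequal ones.

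**6. With the matching variance.** Testing P_Test - 1.5 P_Control = 0 gives a type I error of 2.6% (score) or 2.3% (Wald). Power at 146, 160 and 200 per arm is 61.9%, 65.5% and 75.3% (score), or 59.3%, 63.5% and 73.5% (Wald). For 80%: 0.21 × 3.25 × (1.96 + 0.842)² / 0.15² = 238.1, so 239 per arm, 478 in total.

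**The case against.** The strongest reply is that hypothesis and rule use the same observed rate and so agree with each other. A false claim against H0 as literally written needs the upper limit to be below 0.5 p_C (observed) while the true difference is at or above it. The interval must then lie wholly below the true difference, which happens about 2.5% of the time at most. At 30% vs 45% the enumerated frequency is under 0.1%. A reader might infer that the plan's type I error is 5.9% whatever the hypothesis means; the document does not support that. The figure depends on taking the margin as 50% of the true Control rate.

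That concession does not rescue the rule. A null hypothesis that moves with the sample fixes no set of true rates for which an error rate can be stated. Section 4.3 does fix one: at 30% Control, a relative 50% and an absolute 15 points both put the boundary at 45%, and there the rule accepts about 6% of the time.

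Three further points stand.
- A risk-ratio score interval with limit 1.5 might be taken as the same test. It is when unstratified, but a stratified version assumes a common ratio and uses different weights from the common risk difference in Section 10.1.1.
- A fixed 15-point margin might be taken as a free repair. It is a different criterion. With Control below 30% it accepts a 50% relative increase more often than the present rule does: at 20% vs 30%, about 17%, 18% and 21% at 146, 160 and 200 per arm, against 5.6 to 5.7% now.
- The superiority step (upper bound below 0) does not use the random limit and is unaffected.

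Reading the two-sided 0.05 as 5% on the upper side would not help either, since about 6% exceeds that too.

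**Conclusion.** The point holds, conditional on the margin being half of the true Control rate. On that reading the one-sided type I error is about 5.9 to 6.0% at 30% vs 45% with 146 to 200 per arm, and about 5.6 to 6.5% for Control rates from 20% to 40%. The upper bound of a two-sided 95% interval implies 2.5%.

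Section 4.3 does not describe the planned test. Under the Section 10.1.1 rule, power at 292 subjects is about 75%, not 80% or more. It is about 78% at 320 and 85% at 400.

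The main figures rest on unstratified enumeration; simulations with assumed strata agree. Because this affects the primary claim and can be corrected in text and code, it should be settled before unblinding.

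**What to change.** **Preferred.** In Section 10.1.1, replace the observed rate in H0 and HA by the parameter P_Control. Declare non-inferiority only if the upper limit of the two-sided 95% interval for P_Test - 1.5 P_Control is below 0. Apply the same stratum weights to both arms as in the primary analysis, and use the variance Var(p_T) + 2.25 Var(p_C), summed over strata with squared weights. State whether the score or the Wald form is used. Restate the power in Section 4.3 as about 62%, 66% and 75% at 292, 320 and 400 subjects (score), or about 59%, 63% and 73% (Wald).

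The cost in text and code is small; the cost in power is not. About 478 subjects would be needed for 80%, above the stated ceiling of 400, so the sponsor must either accept the lower power or enlarge the trial. A stratified risk-ratio score limit of 1.5 is a related option, provided that its common-ratio assumption and different weights are stated.

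**Alternative.** Before unblinding, fix the margin at the absolute 15 points for which Section 4.3 was sized. Type I error is then about 2.5% and power about 80% at 292. Section 12 should say that the criterion changes from relative to absolute, that this follows the blinded interim analysis in Section 7.4, and that with a Control rate below 30% the new criterion is more lenient towards a 50% relative increase (about 17 to 21% acceptance at 20% vs 30%).
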